2.2. Rationale

Antiviral therapeutic interventions that reduce infectious virus production could play a key role in decreasing community transmission, decreasing surge on healthcare facilities, and potentially reduce clinical complications of infection. This "treatment as prevention" approach has the potential to reduce the burden of COVID-19 illness and mitigate ongoing transmission. Given the current therapeutic landscape and limitations, there is an urgent need for an orally available direct acting antiviral.

[figure not shown]
EIDD-2801 is the 5'-isobutyrate prodrug of the broadly active, direct acting antiviral ribonucleoside analogue EIDD-1931, which inhibits replication of multiple viral pathogens from multiple RNA families. Further clinical information is needed to determine safety, tolerability, and antiviral activity in humans.

2.3. Preclinical Data

2.3.1. Mechanism of Action

[figure not shown]
The primary mechanism of action of EIDD-2801 is inhibition of viral RNA replication by incorporation of the EIDD-1931-5'-monophosphate metabolite into the viral RNA genome resulting in induction of viral error catastrophe. Upon incorporation into nascent chain RNA, EIDD-1931-5'-monophosphate induces increased mutational frequency in the viral genome resulting in the production of non-viable virus. Following oral delivery, EIDD-2801 is rapidly hydrolyzed by circulating esterases to produce high circulating plasma levels of EIDD-1931 which is in turn phosphorylated into a tri-phosphate (EIDD-2601) that can pair with either guanosine or adenosine and can substitute for either CTP or UTP, respectively, resulting in an accumulation of

[figure not shown]
mutations that increase with each cycle of viral replication ²¹. Additionally, the active metabolite, EIDD-1931-5'-triphosphate, may act as a chain terminator and arrest viral replication via a next nucleoside effect. Given this dual mechanism of action, it is anticipated that there will be a high barrier to the development of resistance.

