1.3. Secondary Objectives

- 1.3.1. To determine if EIDD-2801 reduces the time (days) to negativity of infectious virus isolation in NP swabs from SARS-CoV-2-infected adults. Infectious virus isolation is determined by isolation in Vero cell line culture.
- 1.3.2. To compare the incidence of grade 2 or higher AEs and drug-related AEs between treatment arms.
- 1.3.3. To determine if EIDD-2801 reduces the shedding of SARS-CoV-2 RNA in NP swabs compared to placebo as measured by median change in RNA at Treatment Days 3, 5, 7, 14, and 28 as determined by quantitative RT-PCR.
- 1.3.4. To determine if EIDD-2801 increases viral RNA mutation rate. RNA mutation rate is measured by Next Generation sequencing.
- 1.3.5. To determine if EIDD-2801 changes the severity and duration of self-reported symptoms of COVID-19.
- 1.3.6. To determine if EIDD-2801 treatment reduces the proportion of participants who are hospitalized for COVID-19 related illness by Day 28.
- 1.3.7. To characterize the PK of EIDD-2801/EIDD-1931 in patients with COVID-19 following administration of study regimen.

1.3.8. To determine the relationship between drug exposure and viral elimination dynamics including time to clearance.

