The distribution of days until SARS-CoV-2 is not detectable can be compared between the two trial arms (drug vs. placebo) using an exact stratified log-rank test. At 0.10 (10%) type I error probability and under the assumptions in Figure 9 and the corresponding table below, there is 90% power if the evaluable sample size is 19 individuals per arm in Part 1. In Part 1, anticipating up to 10% missing data, enrolling n=44 participants (approximately 22 per arm) will provide 90% power for the secondary virologic endpoint of time to non-detectable SARS-CoV-2 in NP swabs. Power was calculated empirically in R version 3.6.2 using 5000 simulated datasets.

[figure not shown]

Figure 9: Probability of detectable SARS-CoV-2 assumed in power/sample size determination

	D1	D2	D3	D4	D5	D7	D10
NP swab	Y	Y	Y	Y	Y	Y	Y
Placebo	100%	85%	70%	55%	40%	10%	0%
arm							
EIDD-	100%	50%	35%	20%	5%	0%	0%
2801 Rx							
arm							

Cumulative probability of infectious virus isolation*

Abbreviations: D = Day; NP = nasopharyngeal; Rx = treatment; Y = yes.

Assumes treatment starts 3 to 4 days (i.e., 72 to 96 hours) after symptom onset. NP=nasopharyngeal.

*Extrapolated from Wolfel, R et al. Nature 2020

Reductions in shedding of SARS-CoV-2 RNA in NP swabs at Treatment Days 3, 5, 7, 14, and 28 will also be compared between arms via stratified Wilcoxon rank-sum tests.

Mutation rate (number of mutations in the viral genome) will be assessed using next generation deep genome sequencing (NGS). Mutation rates will be summarized with descriptive statistics and compared between study arms (drug versus placebo).

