9.2. RNA Sequencing

Comparison of RNA dependent RNA polymerase gene sequences will be provided using Next Generation sequencing, amino acid mutations and nucleotide changes based on the detection of changes that occur at $\geq 1\%$ will be flagged by subject and visit.

Treatment emergent mutations are defined as mutations that are not present at baseline. The number and percent of subjects with treatment emergent mutation at each amino acid position will be summarized by treatment group. The data will be presented separately based on the detection of changes occurring at $\geq 1\%$, $\geq 3\%$ or $\geq 10\%$. The between treatment group comparisons will be performed using a 2 sample test based on the average number of treatment emergent mutations.

Treatment emergent nucleotide changes are defined as nucleotide changes that are not present at baseline. The number and percent of subjects with treatment emergent nucleotide change at each amino acid position will be summarized by treatment group. The data will be presented separately based on the detection of changes occurring at $\geq 1\%$, $\geq 3\%$ or $\geq 10\%$. The between treatment group comparisons will be performed using a 2 sample test based on the average number of treatment emergent nucleotide changes.

The results of mutation analysis of SARS-CoV-2 nucleotide sequences compared to the reference SAS-CoV-2 Virus will be summarized by treatment and study visit. The results of mutation analysis of the post baseline vs. the baseline SARS-CoV-2 nucleotide sequences will be summarized by treatment. The data will be presented separately based on the detection of changes occurring at $\geq 1\%$, $\geq 3\%$ or $\geq 10\%$.

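### The mutation objective is tested only on counts of all change types, with no by-type comparison to tell the drug's expected transitions from other changes or from noise that differs between arms

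*Protocol*

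**What the plan says.** Protocol 2.3.1 (Mechanism of Action) says that the incorporated metabolite "induces increased mutational frequency in the viral genome", and that the triphosphate "can pair with either guanosine or adenosine and can substitute for either CTP or UTP". As a further possibility, the triphosphate "may act as a chain terminator and arrest viral replication via a next nucleoside effect".

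Protocol 1.3.4 makes the effect on mutation a secondary objective: "To determine if EIDD-2801 increases viral RNA mutation rate". Protocol 10.7.3.2 gives the measure: "Mutation rate (number of mutations in the viral genome) will be assessed using next generation deep genome sequencing". It promises descriptive summaries and a comparison between arms, and names no type of change.

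SAP 9.2 (RNA Sequencing) compares arms with a "2 sample test based on the average number of treatment emergent mutations" for amino acids and a "2 sample test based on the average number of treatment emergent nucleotide changes" for nucleotides. The test is not named. Changes already present at baseline are excluded, and results are shown at cut-offs of 1%, 3% and 10%, none of which is named as the main one. The text gives no breakdown by substitution type and no adjustment for viral load or read depth. Table shells are in a separate document (SAP 12.1), so a by-type display may exist there, but the SAP text contains no by-type comparison.

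**The concern.** A molecule that stands in for C or U and is read opposite either G or A produces C<->U changes on one strand and G<->A on the other. These are the 4 transitions among the 12 possible substitutions. The section describes no misincorporation route to the 8 transversions, and chain termination is described as stopping replication, not as a source of substitutions.

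Pooling all types has two consequences:

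- **Power.** Changes unrelated to the drug add variance without adding signal.
- **Interpretation.** The drug is expected to lower viral RNA. If samples with less RNA yield a different number of spurious minor variants, the arms could differ in total count with no mutagenesis at all. Transversions from the same samples could reveal this, but the plan does not use them.

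The answer to objective 1.3.4 is at stake: either a missed effect, or a difference that cannot be attributed to the stated mechanism.

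**Working it through.** The documents state no power or effect size for the mutation objective, so there is no figure of the plan to reproduce. The calculations show what the choice of count does under stated assumptions.

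**Inputs from the documents.** 19 evaluable per arm (Protocol 10.5); two-sided alpha 0.10 in Part 1 (Protocol 10.7.3), critical value 1.645.

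**Assumed inputs.** Independent Poisson counts; mean of 3 background changes per participant; background transition share p = 1/3, 0.5 or 0.7; the drug doubles transitions.

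**Step 1: power by choice of count.** The signal is d = 3p for every count below.

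- All changes: active mean 3 + 3p, placebo mean 3, so SE = sqrt((6 + 3p)/19).
- Transitions only: active mean 6p, placebo mean 3p, so SE = sqrt(9p/19).
- Transitions minus transversions: the variances of independent counts add, so SE is again sqrt((6 + 3p)/19).
- Power = Phi(d/SE - 1.645).

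| p | d | SE, all or difference | SE, transitions | Power, all | Power, transitions | Power, difference |
|---|---|---|---|---|---|---|
| 1/3 | 1.0 | 0.607 | 0.397 | 0.50 | 0.81 | 0.50 |
| 0.5 | 1.5 | 0.628 | 0.487 | 0.77 | 0.92 | 0.77 |
| 0.7 | 2.1 | 0.653 | 0.576 | 0.94 | 0.98 | 0.94 |

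The transition-only statistic is 1.53, 1.29 and 1.13 times the all-change statistic. The gain belongs to the transition-only test; the difference contrast has exactly the power of the all-change test.

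**Step 2: a ratio contrast.** For the log ratio of transitions to transversions between arms, SE = sqrt(1/(19 x 6p) + 1/(19 x 3p) + 2/(19 x 3(1 - p))) = 0.363, 0.350 and 0.393, against a signal of ln 2 = 0.693. Power is about 0.60, 0.63 and 0.55, below the all-change test at p = 0.5 and 0.7.

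**Step 3: sensitivity to other assumptions.** Take 22 per arm, a mean of 4 background transitions and a 1.5-fold rise. Power on transitions is 91%. On all changes it falls from 86% to 42% as transversions go from 0.25 to 4 times the transition background. With overdispersed counts (variance mu + 0.5 mu^2), 47% falls to between 44% and 13%. With a 2-fold rise and Poisson counts, the loss is small: from 100% to 88% at worst.

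**Step 4: noise that differs between arms.** Simulation with no drug effect, a background mean of 4 transitions and 4 transversions, extra changes in the active arm only, and a Welch t-test (20,000 runs per setting). Ranges cover noise shares of 1/3, 1/2 and 2/3 falling on transitions.

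| Setting | All changes | Transitions only | Difference |
|---|---|---|---|
| Part 1 (22 vs 22, nominal 10%), 1 extra change | 29-31% | 15-28% | 10-12% |
| Part 1, 2 extra changes | 70-71% | 27-64% | 10-19% |
| Parts 2-9 (96 vs 32, nominal 5%), 1 extra change | 39-40% | 14-35% | 5-9% |

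The difference contrast holds its level when noise splits evenly between the two classes, and drifts above it otherwise.

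**Step 5: does low input raise false calls?** Assume an error of 1e-5 to 1e-4 per base; false calls per 1,000 bases = 1000 x P(Binomial(N, e) >= 0.01N). At N = 100 genomes this is 1 to 10. At N = 101, where two erroneous copies are needed, it is 0.0005 to 0.05. At N = 20 it is 0.2 to 2. At N = 100 with the 3% cut-off it is at most 0.0002. The relation is not monotone, so the direction of any bias is not established.

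**The case against.** The strongest reply is that the SAP answers the question the protocol asks. The objective concerns mutation rate, and Protocol 10.7.3.2 defines that as a number of mutations, so a total count is the right measure and a transition count is a narrower, mechanistic one. This stands: the all-change comparison should not be demoted.

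It can also be said that the SAP already has noise controls: a concurrent randomized placebo arm, exclusion of baseline changes, and repeat displays at 3% and 10%. A reader might infer that the plan has no control at all; the SAP does not support that. These controls are partial, however. Exclusion of baseline changes does not address differences that arise after baseline, and with no main cut-off a result seen only at 1% could be reported as positive.

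A reader might also take Protocol 2.3.1 to say that the drug causes only transitions. It does not. It names no substitution class, uses permissive wording, and speaks generally of raised mutation frequency. The restriction is an inference from base pairing.

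Lastly, Part 1 is the least favourable data set. SAP 5 also plans pooled analyses. With 118 active and 54 placebo participants (Protocol 3), alpha 0.05 and the Step 1 assumptions, the all-change test has power 0.92, 0.998 and above 0.99. That is true, but those analyses involve no formal hypothesis test (Protocol 10.8), and a larger sample does not help interpretation if noise differs by arm.

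**Conclusion.** The point holds as a limited one. SAP 9.2 pools all substitution types although the protocol's own mechanism points, by inference, to transitions, and no pre-specified comparison separates a drug effect from noise that differs between arms after baseline.

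Under the Step 1 assumptions a transition-only test raises power from 0.50, 0.77 or 0.94 to 0.81, 0.92 or 0.98. The true size cannot be found from the documents, which give no background counts, transition shares, overdispersion, sequencing error rates or input amounts; under other assumptions the gain runs from almost nothing to about half the power.

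It would be tempting to claim that one analysis delivers both the power gain and the protection against noise. It does not: transitions alone gain power but remain exposed to noise, while the difference contrast is more robust but gains no power. It would also go too far to say that lower viral load in the active arm must produce more false calls; that noise differs by arm, and in which direction, is assumed. No stated figure is contradicted, only one secondary objective is affected, and the primary endpoint is untouched.

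**What to change.** Amend SAP 9.2 as follows:

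- Keep the between-arm comparison of all treatment-emergent changes, as the measure the protocol defines.
- Add a pre-specified between-arm comparison of treatment-emergent transitions (C<->U, G<->A) at one named main frequency threshold.
- Report the same comparison for transversions from the same samples as a negative control.
- State that a rise will be attributed to the drug's mechanism only when it is not matched by a similar absolute rise in transversions, judged on transitions minus transversions and not on a ratio.

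The cost is one extra classification of sequence data already collected and one extra test without multiplicity adjustment; no new samples are needed. The attribution step has lower power than the transition-only test, and it protects less well if noise falls unevenly on the two classes. The SAP should say so.

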2.3.2. In Vitro Evidence

Antiviral activity of EIDD-2801 against coronaviruses including MERS-CoV, SARS-CoV, SARS-CoV-2, and related zoonotic group 2b or 2c Bat-CoVs has been demonstrated in a number of different tissue culture cell lines including primary human airway epithelial cell cultures⁴. Using a clinical isolate of SARS-CoV-2, EIDD-1931 exhibited an average half-maximum inhibitory concentration (IC₅₀) of 0.3 μ M and a 50% cytotoxic concentration (CC₅₀) of >10 μ M (Figure 5) ⁴. A dose-dependent reduction in infectious virus titers was observed during treatment in a human lung epithelial cell line, Calu-3 cells infected with SARS-CoV-2 with an IC₅₀ of 0.09 μ M. A dose-dependent reduction in SARS-CoV-2 infectious virus production was also found for EIDD-1931 in primary HAE cell cultures without appreciable alteration of host gene expression at doses up to 100 μ M (Figure 6)⁴. Similar results were found for MERS-CoV- and SARS-CoV-infected cell lines and primary HAEs ⁴.

2.4. Evidence in Humans

EIDD-2801 has not been used prophylactically or therapeutically in patients with COVID-19; however, EIDD-2801 has been studied in a single and multiple ascending dose study in healthy volunteers (Study EIDD-2801-1001). Preliminary data from this study showed that doses of 200 mg produce plasma levels of EIDD-1931 that are predicted to show antiviral activity in humans. A brief summary of safety information from Study EIDD-2801-1001 is provided in Section 2.6.

2.5. **Potential Risks and Benefits**

There remains unmet medical need for the treatment of COVID-19, particularly in outpatients where intravenous administration of antiviral therapy is difficult. Participants in this study will be monitored throughout the 5-day treatment course and follow-up period with surveillance for and reporting of all AEs.

2.5.1. Risks Associated with EIDD-2801

Novel therapies can lead to unexpected, incidental findings that could have a potential effect on the participant's health.

Enrollment in a Phase I study of EIDD-2801 (Study EIDD-2801-1001) in 130 healthy volunteers has completed. No serious AEs were reported and no trends of increased frequency or severity of AEs with higher doses of EIDD-2801 were observed. No clinically significant findings or dose-related trends were observed in clinical laboratory, vital signs, or electrocardiogram (ECG) data.

Further details for EIDD-2801-1001 are provided in Section 2.6.

Ongoing surveillance for AEs will be conducted throughout the present study and other ongoing studies, and in the event of confirmation of a potential health effect, the study team will notify participants and will advise appropriate medical follow up when indicated.

EIDD-2801 and EIDD-1931 were shown to be mutagenic (Ames positive) in a bacterial mutagenesis assay with and without metabolic activation.

Given the anticipated short-duration of treatment for COVID-19 (eg, 5 days), EIDD-2801 is considered to have a benefit/risk profile that supports further clinical development.

2.5.2. Risks of Nasopharyngeal Sampling

This procedure will be nurse-administered on Days 1, 3, 5, 7, 14, and 28. Temporary discomfort is associated with this routine medical diagnostic procedure with no reported risk.

2.5.3. Risks of Self-Nasal Mid-Turbinate Swab Sampling

For participants enrolled at applicable sites only, this optional procedure may be self-administered on Days 1, 3, 5, 7, 14, and 28. No reported risks are associated with this procedure.

2.5.4. Risks of Oropharyngeal Sampling

For participants enrolled at applicable sites only, this optional procedure may be nurseadministered on Days 1, 3, 5, 7, 14, and 28. Temporary discomfort is associated with this routine medical diagnostic procedure with no reported risk.

2.5.5. Risk of Blood Collection

Blood collection may cause pain, bruising, and occasionally a feeling of lightheadedness or fainting. Rarely, it may be associated with an infection at the site of blood drawing.

2.5.6. Risks of Pregnancy and Use in Nursing Women

Treatment with EIDD-2801 is contraindicated in women who are pregnant or nursing and in the male partners of women who are pregnant. Extreme care must be taken to avoid pregnancy during the study and for 50 days after completion of EIDD-2801 dosing in female participants and for 100 days after completion of EIDD-2801 dosing in female participants.

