4. SELECTION AND ENROLLMENT OF PARTICIPANTS

4.1. Inclusion Criteria

- 4.1.1. Able to provide informed consent prior to initiation of any study procedures.
- 4.1.2. ≥ 18 years of age at Screening.
- 4.1.3. Study treatment is expected to begin within ≤ 168 hours from first symptom onset.
- 4.1.4. Ability to swallow pills
- 4.1.5. Documentation of confirmed active SARS-CoV2 infection, as determined by a molecular or non-molecular ("rapid") test conducted at any clinic or laboratory that has a Clinical Laboratory Improvement Amendments (CLIA) certification or its equivalent from a sample collected ≤96 hours prior to study entry.
- 4.1.6. Experiencing at least one of the following SARS-CoV-2 infection symptoms at the time of enrollment: fever (can be subjective including feeling feverish or having chills) OR signs/symptoms of respiratory illness (including but not limited to upper respiratory congestion, loss of sense of smell or taste, sore throat OR lower respiratory illness cough, shortness of breath).
- 4.1.7. Agrees to not participate in another interventional clinical trial for the treatment of SARS-CoV-2 during the study period (28 days) unless hospitalized.
- 4.1.8. Agrees to not obtain investigational medications outside of the EIDD-2801 study.
- 4.1.9. Agrees to the sampling detailed in the SOE and to comply with study requirements including contraception requirements.

- 4.1.10. A female participant is eligible to participate if she is not pregnant or breastfeeding and at least one of the following conditions applies:
 - Is not a woman of childbearing potential (WOCBP)

OR

- Is a WOCBP and using a contraceptive method that is highly effective (a low user dependency method OR a user-dependent method in combination with a barrier method), or be abstinent from heterosexual intercourse as their preferred and usual lifestyle (abstinent on a long-term and persistent basis), as described in Appendix 2 during the intervention period and for at least 50 days after the last dose of study intervention. The investigator should evaluate the potential for contraceptive method failure (ie, noncompliance, recently initiated) in relationship to the first dose of study intervention.
- A WOCBP must have a negative highly sensitive pregnancy test (serum or urine) within 24 hours before the first dose of study intervention.
- Additional requirements for pregnancy testing during and after study intervention are located in Section 6.2.15.

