- The investigator is responsible for review of medical history, menstrual history, and recent sexual activity to decrease the risk for inclusion of a woman with an early undetected pregnancy.
- Contraceptive use by women should be consistent with local regulations regarding the methods of contraception for those participating in clinical studies.
- Given the elevated risk of venous thrombotic events in patients hospitalized with COVID-19^{22,23}, estrogen-containing contraceptives must not be started to fulfill the contraceptive requirement of this study at any time during participant's hospitalization. If contraceptives are interrupted as standard of care management of COVID-19 patients and resumed at a later time point, such as at hospital discharge, then abstinence must be practiced for the defined period of back-up contraceptive new terms and here to Appendix 2.
- 4.1.11. Male participants are eligible to participate if they agree to the following during the intervention period and for at least 100 days after the last dose of study intervention:
 - Refrain from donating sperm

PLUS either:

• Be abstinent from heterosexual intercourse as their preferred and usual lifestyle (abstinent on a long term and persistent basis) and agree to remain abstinent

OR

• Must agree to use contraception unless confirmed to be azoospermic (vasectomized or secondary to medical cause [Appendix 2]) as detailed below: Agree to use a male condom plus partner use of an additional contraceptive

method when having penile-vaginal intercourse with a WOCBP who is not currently pregnant. Note: Men with a pregnant or breastfeeding partner must agree to remain abstinent from penile-vaginal intercourse or use a male condom during each episode of penile-vaginal penetration.

• Contraceptive use by men should be consistent with local regulations regarding the methods of contraception for those participating in clinical studies.

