7.3. Reporting Requirements for this Study

The PI or clinical site personnel should notify Covance PSS of all SAEs, regardless of relationship to the investigational drug, within 24 hours of clinical site personnel becoming aware of the event. The PI (or designee) will provide the initial notification by sending a completed SAE form which must include the PI's (or designee's) assessment of the relationship of the event to investigational drug and must be signed by the PI. Follow-up information, or new information regarding an ongoing SAE, must be provided promptly to Covance DSS at the study agents for which expedited reporting are required are:

• EIDD-2801 or Placebo for EIDD-2801

The investigator will attempt to establish a diagnosis of the event based on signs, symptoms, and/or other clinical information. Whenever possible, the diagnosis (not the individual signs/symptoms) will be documented as the AE/SAE.

Additionally, all reported pregnancies from the day of randomization through 50 days (for female participants) or 100 days (for female partners of male participants) after the last dose of study intervention must be reported to the sponsor by the investigator.

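### Protocol 2.5.6 contraindicates treatment in men whose partner is pregnant, while inclusion criterion 4.1.11 provides for such men on conditions and no exclusion criterion in 4.2 bars them

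*Protocol*

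**What the plan says.** On men whose partner is pregnant, two places in the protocol speak directly.

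- Section 2.5.6, within the account of risks and benefits: "Treatment with EIDD-2801 is contraindicated in women who are pregnant or nursing and in the male partners of women who are pregnant".
- Section 4.1.11, within the inclusion criteria. It opens with "Male participants are eligible to participate if they agree to the following during the intervention period and for at least 100 days", counted from the end of dosing. Its note on partners reads "Men with a pregnant or breastfeeding partner must agree to remain abstinent from penile-vaginal intercourse or use a male condom during each episode".

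Section 4.2 lists the exclusion criteria. None refers to a participant's partner.

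On the period for avoiding pregnancy, the second sentence of 2.5.6 gives it as "for 50 days after completion of EIDD-2801 dosing in female participants and for 100 days after completion of EIDD-2801 dosing in female participants". Criterion 4.1.10 asks women of childbearing potential for contraception "during the intervention period and for at least 50 days after the last dose of study intervention". Criterion 4.1.11 and section 2.10 attach 100 days to men. Section 7.3 sets the pregnancy reporting window at "50 days (for female participants) or 100 days (for female partners of male participants").

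**The concern.** A contraindication is a statement about who may be treated. Section 2.5.6 puts men with a pregnant partner in that group without qualification. The note in 4.1.11 tells the same men what they must agree to in order to qualify, and it would have little purpose at screening if they could not be enrolled. An investigator who reads section 4 alone may enrol and dose such a man if he accepts the condition. An investigator who also reads 2.5.6 would turn him away.

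Different sites could therefore handle the same candidate differently and each point to the protocol. Any consequence would fall mainly on a partner and fetus, who are not themselves enrolled. No endpoint or analysis is involved.

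**Working it through.** No arithmetic applies. The check compares the passages and then looks for any other text that settles the matter.

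**Step 1: the two statements on men with a pregnant partner**

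| Place | Status of a man with a pregnant partner | Condition |
|---|---|---|
| 2.5.6 | Treatment contraindicated | None stated |
| 4.1.11 | Provided for among eligible men | Abstinence or condom use |
| 4.2 | Not mentioned | Not applicable |

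Criterion 4.1.11 separates two situations. One requirement covers intercourse with a woman of childbearing potential who is not pregnant at the time, and the note covers a pregnant or breastfeeding partner. The pregnant-partner case was therefore considered when the criterion was written.

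**Step 2: does other text resolve it?**

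- Criterion 4.2.14 excludes people whose condition puts the participant at increased risk. It does not reach risk to a partner or fetus.
- Section 2.10 sends men with female partners to Appendix 2. That appendix defines childbearing potential and lists contraceptive methods. It says nothing about men whose partner is already pregnant.
- Sections 8.6 and 8.7 bar giving study product in pregnancy and to breastfeeding women. Neither mentions male partners.
- Section 9.1 lists pregnancy among the reasons for stopping treatment, without saying whether a partner's pregnancy counts.
- Sections 7.3 and 7.3.5 require a partner's pregnancy to be reported and followed. They do not address eligibility or dosing.
- No section states that one of 2.5.6 and section 4 takes precedence over the other.

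Nothing removes the conflict found in step 1.

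**Step 3: the 50-day and 100-day periods**

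| Place | 50 days attached to | 100 days attached to |
|---|---|---|
| 2.5.6 | Female participants | Female participants |
| 2.10 | Not stated | Male participants (sperm donation) |
| 4.1.10 | Women of childbearing potential | Not stated |
| 4.1.11 | Not stated | Male participants |
| 7.3 | Female participants | Female partners of male participants |

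As printed, 2.5.6 gives women two periods and men none. The other four places are consistent with one another in dividing the periods by sex, so 2.5.6 is the outlier.

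**The case against.** Four counter-arguments deserve an answer.

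*Section 2.5.6 is background, and sites screen against section 4.* The sections do differ in function, and this reduces the likely confusion. It does not remove the conflict. The protocol gives section 4 no precedence, and a contraindication is not mere background. Following section 4 alone is exactly how a man covered by 2.5.6 would come to be dosed.

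*The note in 4.1.11 may concern a partner's pregnancy that begins after enrolment.* The commitment runs through treatment and at least 100 days beyond it, so the note can apply to that case. It is not confined to it, however. It sits in an eligibility criterion and contrasts with the rule for partners who are not currently pregnant. A partner's pregnancy that came to light during the five treatment days would also raise the same question under 2.5.6.

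*A site can comply with both passages by declining the man.* This stands. A reader might infer that no site could satisfy both statements, but the documents do not support that: 4.1.11 sets conditions and does not oblige anyone to enrol a candidate. What the text supports is narrower, namely that the two passages answer differently whether he may be enrolled and dosed.

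*The duplicated reference to female participants is a wording slip.* It reads as one. A reader might infer real uncertainty over how long women must use contraception. The criterion that a site applies to women, 4.1.10, states a single period and 7.3 agrees with it, so no ambiguity in conduct is shown. For that reason it is treated here only as a minor correction.

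Two further inferences are tempting. One is that participants receive a faulty risk statement. The consent form was not available for review, so no claim is made about it. The other is to tie the conflict to the positive bacterial mutagenesis result in 2.5.1. The visible text does not link that result to exposure of a pregnant partner, and the point does not depend on it.

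**Conclusion.** The point holds as an internal contradiction about who may be treated. Section 2.5.6 bars treatment in men with a pregnant partner without condition, 4.1.11 provides for them on condition, and 4.2 does not carry the bar.

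Its size cannot be put into numbers, because the documents do not say how many candidates would have a pregnant partner. It touches each such man who is screened and may be few people. It has no effect on sample size, power, type I error or any planned analysis. It merits correction because it concerns treatment eligibility and the safety of people outside the trial.

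The conclusion assumes that the note in 4.1.11 applies at entry, which is its natural reading though not the only possible one. The wording of the two periods in 2.5.6 is a secondary matter, already settled for conduct by the other sections.

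**What to change.** Reconcile 2.5.6 with 4.1.11 and 4.2 so that a single rule governs whether men with a pregnant partner may be enrolled and dosed, and state it identically wherever it appears. Which rule that should be is for the sponsor's clinical and safety experts, and this review takes no position.

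In the same edit, reconcile the sentence in 2.5.6 that gives the 50-day and 100-day periods with 2.10, 4.1.10, 4.1.11 and 7.3.

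The cost is protocol wording. No statistical section needs to change.
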